PI'S STATEMENT OF APPROVAL

Confidentiality of all information received or developed in connection with this protocol will be maintained by me, as well as all other personnel involved in the study who are employed by me. By signing this protocol, I confirm that I have read and agree to conduct the study as outlined in the protocol and in compliance with Good Clinical Practice, the Declaration of Helsinki as amended and all other applicable regulatory requirements.

Printed name of PI: _____

Signature

Date

CONFIDENTIAL

STUDY CONTACT INFORMATION

Sponsor :

Synaptogenix, Inc.
[name]
[name]
[name]
[contact]
[contact]

[name]

Chief Medical Officer
Synaptogenix, Inc.
[contact]
Email [contact]

[name]

Executive Director, Clinical Operations
Synaptogenix, Inc.
[contact]
Email: [contact]

Study Administrative Structure

Clinical Research Organization

Worldwide Clinical Trials

Operational Headquarters
[name]
[name]
[contact]
Corporate Headquarters
[name]
[name]
[contact]

Study Medical Monitor/Emergency Contact
Information

[name], PhD
Worldwide Clinical Trials
[contact]
Email: [contact]

Central Laboratory

ACM Global Laboratory
[name]
[name]
[contact]

Central ECG

Clario (formerly ERT)
[name]
[name]
[contact] ERT

PROTOCOL SYNOPSIS

Name of Company: Synaptogenix, Inc.	Name of Study Medication: Bryostatin 1	Name of Active Ingredient: Bryostatin 1
Title of Study: A Randomized, Double-Blind, Placebo-Controlled, Confirmatory Phase 2 Study Assessing the Safety, Tolerability and Long-term Efficacy of Bryostatin in the Treatment of Moderately Severe Alzheimer’s Disease Subjects Not Receiving Memantine Treatment		
Study center(s): Approximately 20 sites in United States (US)		
Protocol Number: NTRP-101-204		
Study Duration: Approximately 2 years	Study Phase: 2	
Objective: Primary objective: To evaluate the safety, tolerability, and long-term efficacy of bryostatin 1 (hereafter referred to as bryostatin) for the treatment of moderately severe Alzheimer’s disease (AD).		
Study Drug: Bryostatin 1 or matching Placebo		
Route of Administration: Intravenous by continuous infusion over 45±5 minutes		
Number of Subjects: Approximately 100 subjects (approximately 220 subjects screened)		
Study Design This is a randomized double-blind placebo-controlled, Phase 2 study comparing bryostatin-1 to placebo for long-term efficacy in the treatment of moderately severe AD (Mini Mental State Examination, 2 nd edition scores of 10-18 at baseline) in the absence of memantine. Eligible subjects will receive 7 doses of bryostatin (i.v., 20µg) or matching placebo during the first 12 weeks. A second course of treatment consisting of 7 doses will begin 30 days after the final dose of the first treatment period. Cognitive tests will be assessed at intervals during the study and 30 days after the final dose of study drug. The primary endpoint is the total SIB score assessment obtained at Week 28, following completion of 2 courses of treatment. Randomization and Treatment Eligible subjects will be stratified based on baseline SIB total scores and will be randomized 1:1 to one of two treatment arms: 20µg bryostatin or placebo for twelve weeks, the first treatment period. The first two doses of study drug will be a loading dose 20% higher (i.e., 24µg) than the assigned dose and will be administered one week apart. Thereafter, the assigned dose of 20µg will commence with the third dose and be administered every other week. The second course of treatment will be identical to the first, beginning 30 days after		

CONFIDENTIAL

Name of Company: Synaptogenix, Inc.	Name of Study Medication: Bryostatin 1	Name of Active Ingredient: Bryostatin 1

completion of the first course. Drug is administered IV by continuous infusion over 45(±5) minutes. Subjects are scheduled to receive seven doses over 12 weeks during the first treatment period and seven doses over 12 weeks during the second treatment period. The same treatment assigned at randomization will be administered during the second treatment period.
 
Cognitive Assessments
 
 • Severe Impairment Battery (SIB) • Mini Mental State Examination, 2nd edition (MMSE-2) • Alzheimer’s Disease Cooperative Study – Activities of Daily Living - Severe Impairment Version (ADCL-ADL-Sev) • Neuropsychiatric Inventory (NPI) metrics. 
Safety Assessments
 
 • Treatment emergent adverse events (AEs) and Serious Adverse Events (SAEs) • Vital signs, physical examination including body weight • ECG parameters • Columbia Suicide Severity Rating Scale (C-SSRS), and • Clinical laboratory assessments (hematology, blood chemistry) 
Primary Efficacy Endpoint
 
The primary efficacy endpoint is the change from the pre-treatment baseline in the Severe Impairment Battery (SIB) total score at Week 28, after two 12-week courses of treatment.
 
Secondary Efficacy Endpoints
 
 • SIB total score at the end of the Week 42 follow-up visit, for subjects who completed week 42 • SIB total score from baseline at Week 13 • SIB total scores from baseline at Weeks 9, 20, 24 and 30 • SIB total scores from baseline at Weeks 9, 20, 24 and 30 for subjects with baseline MMSE-2 scores of 10-14 and 15-18 • SIB trends over time; individual-specific slopes of total SIB scores will be obtained for all patients. 		

CONFIDENTIAL

Name of Company: Synaptogenix, Inc.	Name of Study Medication: Bryostatin 1	Name of Active Ingredient: Bryostatin 1

Exploratory Efficacy Endpoints
 
 • Change from baseline in ADCS-ADL-Sev total score at Week 13 and Week 42, for subjects who completed week 42 • Change from baseline in MMSE-2 total score at Week 13 and Week 42, for subjects who completed week 42 • Change from baseline in NPI total score at Week 13 and Week 42, for subjects who completed week 42 • 		

Statistical Considerations:
 
The primary objective for efficacy is to evaluate whether bryostatin is better than the control with respect to the primary and secondary SIB endpoints. Efficacy analyses will be conducted for the full analysis set (FAS), consistent with the modified intention-to-treat principle, defined as all randomized subjects who received at least one dose of randomized study medication and who had at least one post-baseline efficacy assessment.
 
The per protocol analysis set (PP) is defined as all patients completing the study without major protocol deviations. To be included, subjects must have received at least 11 of the 14 doses (80%). The completer analysis set (CAS) will be defined as all randomized subjects who completed two 12-week courses of treatment, and who have a Week 28 SIB assessment. Efficacy analyses will also be conducted for the PP and CAS sets.
 
Adverse event and other safety data will be analyzed descriptively in all subjects who received any dose of study drug (including partial infusions). These data will be summarized by treatment group and by time in study.
		

Eligibility Criteria:**Inclusion**

1. Written informed consent from caregiver and subject (if possible) or legally acceptable representative if different from caregiver
2. Male and female subjects 55-85 years of age inclusive
3. Cognitive deficit present for at least 2 years that meet the diagnostic criteria for probable Alzheimer's dementia.¹ The diagnosis must be confirmed at the time of the screening visit
4. MMSE-2 score of 10-18 inclusive (applies to Screening Visit only)
5. Patients must have a baseline SIB total score of at least 60 and may not have a SIB score >93 at screening
6. Neuroimaging computerized tomography (CT) or Magnetic Resonance Imaging (MRI) within the last 24 months consistent with a diagnosis of probable AD without any other clinically significant co-morbid pathologies. If there has been a significant change in the subject's clinical status since the last imaging study that is not consistent with progression of the subject's AD, an imaging study should be performed to confirm eligibility
7. Reliable caregiver(s) or informant(s) who attends the subject at least an average of 3 hours or more per day for 3 or more days per week and who will agree to accompany the subject to the clinic visits and reliably complete the caregiver questions
8. Adequate vision and motor function to comply with testing
9. If taking an approved cholinesterase inhibitor for treatment of Alzheimer's disease, must be on a stable dose for at least 3 months prior to entry into study and the dose must not change during the study unless a change is required due to an adverse effect of the prescribed medication or a clinically significant change in the patient's status
10. Subjects who are memantine naïve or have been off memantine for at least 90 days prior to initial treatment with study drug
11. Subjects on neuroleptic medications must be on a stable dose for ≥ 4 weeks at screening (dose adjustments will be permitted if medically necessary at the discretion of the PI)
12. Females participating in the study must meet one the following criteria:
 - a. Surgically sterilized (e.g., hysterectomy, bilateral oophorectomy or tubal ligation) for at least 6 months or postmenopausal (postmenopausal females must have no menstrual bleeding for at least 1 year) or
 - b. If not postmenopausal, agree to use a double method of contraception, one of which is a barrier method (e.g., intrauterine device plus condom, spermicidal gel plus condom) 30 days prior to dosing until 30 days after last dose and have

CONFIDENTIAL

negative human chorionic gonadotropin (β -hCG) test for pregnancy at screening

13. Males who have not had a vasectomy must use appropriate contraception methods (barrier or abstinence) from 30 days prior to dosing until 30 days after last dose
14. In the opinion of the PI subjects should be in reasonably good health over the last 6 months and any chronic disease should be stable

Exclusion

1. Dementia due to any condition other than AD, including vascular dementia (Rosen-Modified Hachinski Ischemic score ≥ 5)
2. Evidence of significant central nervous system (CNS) vascular disease on previous neuroimaging including but not limited to: cortical stroke, multiple infarcts, localized single infarcts in the thalamus, angular gyrus, multiple lacunar infarcts or extensive white matter injury
3. Clinically significant neurologic disease or condition other than AD, such as cerebral tumor, chronic subdural fluid collections, Huntington's Disease, Parkinson's Disease, normal pressure hydrocephalus, or any other diagnosis that could interfere with assessment of safety and efficacy
4. Evidence of clinically significant unstable cardiovascular, pulmonary, renal, hepatic, gastrointestinal, neurologic, or metabolic disease within the 6 months prior to enrollment. If there is a history of cancer the subject should be clear of cancer for at least 2 years prior to screening. More recent history of basal cell or squamous cell carcinoma and melanoma in situ (Stage 0) may be acceptable after review by the Medical Monitor.
5. Creatinine clearance (CL) of <45 ml/min
6. Poorly controlled diabetes, at the discretion of the Principal Investigator
7. Concomitant treatment with NMDA receptor antagonists such as but not limited to memantine or drug combinations containing memantine, dextromethorphan (a cough suppressant), ketamine, phencyclidine (PCP), methoxetamine (MXE), nitrous oxide (N_2O) and the following synthetic opioids: penthidine, levorphanol, methadone, dextropropoxyphene, tramadol, and ketobemidone.
8. Use of vitamin E > 400 International Units (IU) per day within 14 days prior to screening
9. Use of more than 2,600 mg/day of acetaminophen for more than 3 consecutive days within 14 days prior to screening
10. Use of gabapentin within 14 days prior to screening
11. Use of valproic acid within 14 days prior to screening
12. Use of an active Alzheimer's vaccine within 2 years prior to screening
13. Use of a monoclonal antibody for treatment of AD within 1 year prior to screening

CONFIDENTIAL

14. Any medical or psychiatric condition that is likely to require initiation of additional medication or surgical intervention during the course of the study
15. Any screening laboratory values outside the reference ranges that are deemed clinically significant by the PI
16. Use of an investigational drug within 90 days prior to screening
17. Suicidality defined as active suicidal thoughts during the 6 months prior to screening or at Baseline [Type 4 or 5 on C-SSRS], or history of suicide attempt in previous 2 years, or at serious suicide risk in PI's judgment
18. Major psychiatric illness such as current major depression according to Diagnostic and Statistical Manual of Mental Disorders, 5th Edition², current or past diagnosis of bipolar disorder, schizophrenia, or any other psychiatric disorder that might interfere with the assessments of safety or efficacy at the discretion of the PI
19. Diagnosis of alcohol or drug abuse within the last 2 years
20. Abnormal laboratory tests that suggest an alternate etiology for dementia. If the patient has prior history of serum B12 abnormality, anemia with hemoglobin ≤ 10 g/dl, thyroid function abnormality, electrolyte abnormality, or positive syphilis serology the patient should be reevaluated to determine if these potential causes of dementia have been addressed. Only if these causes have been ruled out as the cause of the dementia can the patient be enrolled.
21. History of prolonged QT or prolonged QT on screening ECG (QTcB or QTcF >499 per central reader)
22. Acute or poorly controlled medical illness: blood pressure > 180 mmHg systolic or 100 mmHg diastolic; myocardial infarction within 6 months; uncompensated congestive heart failure [New York Heart Association (NYHA) Class III or IV]³
23. Known to be seropositive for human immunodeficiency virus (HIV)
24. Known to be seropositive for Hepatitis B or C, unless successful curative treatment for Hepatitis C (e.g., Harvoni) has been received and there is documentation that there is no Hep B/C virus detected 3 months after completion of treatment
25. AST or ALT $>3x$ upper limit of normal (ULN) and total bilirubin $>2x$ ULN or International Normalized Ratio (INR) >1.5
26. Prior exposure to bryostatin, or known sensitivity to bryostatin or any ingredient in the study drug
27. Any other concurrent medical condition, which in the opinion of the PI makes the subject unsuitable for the clinical study

CONFIDENTIAL

Institute on Aging-Alzheimer's Association workgroups on diagnostic guidelines for Alzheimer's disease. *Alzheimer's & Dementia : The Journal of the Alzheimer's Association*, 7:263–9.

American Psychiatric Association. *Diagnostic and Statistical Manual of Mental Disorders*, 5th Edition: DSM-5 – May 27, 2013. American Psychiatric Association. Washington, D.C.

http://www.heart.org/HEARTORG/Conditions/HeartFailure/AboutHeartFailure/Classes-of-Heart-Failure_UCM_306328_Article.jspList of References

Table of Contents

SPONSOR’S SIGNATURE PAGE	2
STUDY CONTACT INFORMATION	4
STUDY ADMINISTRATIVE STRUCTURE	5
PROTOCOL SYNOPSIS	6
1 INTRODUCTION	19
1.0 Alzheimer’s disease	19
1.1 Rationale for the use of bryostatin in the treatment of AD.....	20
1.2 Pharmacokinetics, Toxicology and Drug Metabolism in Animals.....	20
1.3 Genotoxicity.....	21

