6.0.1 Safety

Overall safety and tolerability will be assessed by the incidence of treatment emergent AEs and SAEs and by evaluations of change from baseline in physical examination, vital signs, 12-lead ECG, the C-SSRS, clinical chemistry, hematology, and coagulation lab tests.

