6.1.2 Week 0 (Day 0 Dose 1)

If the subject has had no intervening medical issues or changes in medications between the date of randomization and Week 0, dosing may proceed as scheduled.

A final assessment of the inclusion/exclusion criteria, including any changes in medications or health status will be done before dosing to confirm the subject's eligibility.

The following procedures will be done on Day 0:

- *Dosing by IV infusion* will be done according to the procedures outlined in Section 5.7.
- Vital signs prior to infusion, then at 30(\pm 5), 60(\pm 5) and 90(\pm 5) minutes from start of the infusion

CONFIDENTIAL

- Adverse events and concomitant medications

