6.2.11 Columbia-Suicide Severity Rating Scale (C-SSRS)

The following outcomes are C-SSRS categories and have binary responses (yes / no). The categories have been re-ordered from the actual scale to facilitate the definition of composite endpoints:

Category 1	Wish to be Dead
Category 2	Non-specific Active Suicidal Thoughts
Category 3	Active Suicidal Ideation with Any Methods (Not Plan) without Intent to Act
Category 4	Active Suicidal Ideation with Some Intent to Act, without Specific Plan
Category 5	Active Suicidal Ideation with Specific Plan and Intent
Category 6	Preparatory Acts or Behavior
Category 7	Aborted Attempt
Category 8	Interrupted Attempt
Category 9	Actual Attempt (non fatal)
Category 10	Completed Suicide

Suicidal Ideation since baseline – A “yes” answer at any time during double blind treatment to any one of the 5 suicidal ideation questions (categories 1-5) on the C-SSRS.

QMD Ref: Worldwide-TMP-ST-005-7.0 Effective: 12Aug2019	Governing QMD: Worldwide-SOP-ST-001
Confidentiality Statement	
This document is the property of Worldwide Clinical Trials Inc. and may not be duplicated, copied, altered or removed from company without prior approval from Worldwide Quality Assurance or in compliance with Worldwide Standard Operating Procedures.	

Suicidal Behavior since baseline – A “yes” answer at any time during double blind treatment to any one of the 5 suicidal behavior questions (categories 6-10) on the C-SSRS.

There will be no imputation of missing data for C-SSRS.

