6.12.6 Columbia Suicide Severity Rating Scale

Columbia Suicide Severity Rating Scale (C-SSRS) will be collected at screening, Weeks 2, 7, 13, 18, 26 and 42. Results will be presented in a table with descriptive statistics and in a listing.

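### The SAP's C-SSRS outcomes since baseline set no condition on the pre-dose answer and no shift table is listed, so ideation that persists from screening is counted the same as new ideation

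*Protocol*

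**What the plan says.** **Entry.** Exclusion 17 (Protocol synopsis and section 4.4.2) begins "Suicidality defined as active suicidal thoughts during the 6 months prior to screening or at Baseline [Type 4 or 5 on C-SSRS". A suicide attempt in the previous two years, or serious risk in the investigator's judgment, also excludes.

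**Outcome.** SAP 6.2.11 orders ten C-SSRS categories: 1 to 5 are ideation, 6 to 10 behavior. Ideation since baseline is a yes "answer at any time during double blind treatment to any one of the 5 suicidal ideation questions (categories 1-5) on the C-SSRS". Behavior since baseline is a yes "answer at any time during double blind treatment to any one of the 5 suicidal behavior questions (categories 6-10) on the C-SSRS". Neither definition refers to the pre-dose response.

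**Stated comparison.** Protocol 6.0.1 says safety will be assessed in part by "evaluations of change from baseline in physical examination, vital signs, 12-lead ECG, the C-SSRS" and laboratory tests. SAP 6.2.2 takes the last non-missing pre-dose value as baseline.

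**Presentation.** SAP 6.12.6 plans a descriptive table and a listing. The SAP table list has one C-SSRS table at screening (14.3.7.3) and one at post-baseline visits (14.3.7.4).

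**Timing.** According to SAP 6.12.6 the C-SSRS "will be collected at screening, Weeks 2, 7, 13, 18, 26 and 42". Protocol 6.1.2, under "The following procedures will be done on Day 0", lists dosing, vital signs, adverse events and concomitant medications, but no C-SSRS.

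**The concern.** An outcome labelled as occurring since baseline should separate what began or worsened after the first dose from what was already there. This one does not. A patient who enters at category 1 and reports category 1 again at Week 2 scores the same as a patient who had nothing at screening.

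Safety is part of the primary objective (Protocol 3.0), and the C-SSRS is a named safety assessment (Protocol 4.3.1). No C-SSRS hypothesis is tested (Protocol 9.3), so readers will judge from the counts alone. Carried-over cases raise the rate in both arms and weaken any real contrast. With about 50 patients per arm, they can also differ between arms by chance. Separate group tables for screening and post-baseline cannot show whether the same patients or different ones answered yes.

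**Working it through.** The plan states no figure on this point, so there is none to reproduce. The check sets the passages side by side and then illustrates size under stated assumptions.

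**Step 1. Can such patients enter?** Exclusion 17 names types 4 and 5 only. Types 1 to 3 are not excluded by score.

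**Step 2. Are they counted?** The SAP 6.2.11 definition includes categories 1 to 5 and has no pre-dose condition. Four cases follow:

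| Screening C-SSRS | After dosing | Counted | New or worse |
|---|---|---|---|
| None | Category 1 | Yes | Yes |
| Category 1 | Category 1 | Yes | No |
| Category 1 | Category 3 | Yes | Yes |
| Category 1 | None | No | No |

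The second row is the misclassification.

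**Step 3. Does another planned table separate them?** Shift tables are planned for laboratory data (SAP 6.12.2; Tables 14.3.4.2 and 14.3.4.4), ECG interpretation (SAP 6.12.4; Table 14.3.7.2) and physical examination (SAP 6.12.5). None is listed for the C-SSRS.

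**Step 4. Was the comparison dropped on purpose?** SAP section 9 lists three changes from the protocol: removal of false discovery rate control, a revised visit list for one secondary endpoint, and MMRM in place of GEE. The C-SSRS is not among them. This points to an omission.

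**Step 5. Illustrated size.** Assumptions: 50 patients per arm (Protocol 9.0); a share q of each arm enters with categories 1 to 3 and reports them again after dosing. The documents do not give q.

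- Expected carried-over cases per arm = 50 × q.
- With independent Binomial(50, q) counts X and Y in the two arms, the chance of a difference of three or more from these cases alone is P(|X − Y| ≥ 3).

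| q | Cases per arm | P(\|X − Y\| ≥ 3) |
|---|---|---|
| 1% | 0.5 | 0.018 |
| 2% | 1 | 0.072 |
| 2.5% | 1.25 | 0.103 |
| 5% | 2.5 | 0.242 |
| 10% | 5 | 0.400 |

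These chances are two-sided; by symmetry, half of each goes against bryostatin. Entry rates of 2%, 5% and 10% with full persistence give q = 2%, 5% and 10%. With half persistence, q = 1%, 2.5% and 5%.

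**Step 6. Illustrated dilution.** Assume new-onset rates r of 2% on placebo and 12% on bryostatin. Observed rate = q + (1 − q) × r.

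- q = 0: 12.0% / 2.0% = risk ratio 6.00; difference 10.0 points.
- q = 2%: 13.76% / 3.96% = 3.47; difference 9.8 points.
- q = 5%: 16.4% / 6.9% = 2.38; difference 9.5 points.
- q = 10%: 20.8% / 11.8% = 1.76; difference 9.0 points.

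The risk ratio shrinks markedly; the risk difference barely moves.

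**The case against.** Several points on the other side stand.

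- **A reader might infer that the C-SSRS is never compared with baseline.** The documents do not support that. Protocol 6.0.1 states the comparison, SAP 6.2.2 supplies a baseline, SAP 6.6 summarises the screening C-SSRS by treatment group, and all answers are listed. What is missing is a planned subject-level summary. Even this is read from the definitions and table titles, since no table shells are given.
- **A reader might infer that all ideation before the first dose counts as on-treatment.** It does not. Ideation reported only at screening is not counted; it enters only if a yes is recorded again after dosing. That could also happen if the Week 2 form looks back past the first dose, but the documents do not name the form or its recall period. If it covered the time since the last C-SSRS, the pre-dose share would run from 2/18 = 11% (screening at Day −2, visit on Day 16) to 28/40 = 70% (screening at Day −28, visit on Day 12). No single figure in that range can be relied on.
- **Emergence is partly handled elsewhere.** Protocol 6.0.1.5 has the investigator decide, for any positive C-SSRS response, whether an adverse event occurred, and requires a narrative after a post-baseline risk assessment. Adverse events are classed as treatment-emergent by onset date, and pre-treatment events are listed separately (SAP 6.12.1). This separates new from old only for responses judged to be adverse events; the C-SSRS counts remain mixed.
- **Numbers may be small.** Serious risk and major psychiatric illness exclude, and the C-SSRS is reviewed centrally before randomization (Protocol 6.1.1). The summary of study NTRP101-202 (Protocol 2.1.2.3) says most subjects had no suicidal thoughts and reports no group differences. Randomization balances entry ideation in expectation, and the screening summary by arm would reveal a gross imbalance.
- **A reader might treat the absence of a Day 0 C-SSRS as the main defect.** It is secondary. The documents elsewhere equate baseline with screening (Protocol 4.3.3 and 9.5.3), and Protocol 6.1.2 rechecks eligibility: "A final assessment of the inclusion/exclusion criteria, including any changes in medications or health status will be done before dosing". A pre-dose value exists and can serve as the comparator.

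**Conclusion.** The point holds in limited form. The two since-baseline outcomes in SAP 6.2.11 are not conditioned on the pre-dose C-SSRS, and the SAP lists no shift table to make good the change from baseline that Protocol 6.0.1 states. Persisting low-grade ideation is therefore classified as if it were new.

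The size is unknown because the documents give no rate of types 1 to 3 at entry and no rate of persistence. Every number above is illustrative and rests on assumed rates. The consequence is confined to a descriptive safety summary. It is worth correcting because safety is in the primary objective and the remedy needs no new data. The wording of exclusion 17 is a separate, minor reconciliation.

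**What to change.** 1. In SAP 6.2.11, add a treatment-emergent definition: the highest post-baseline ideation category exceeds the highest pre-dose category, or ideation is present when none was before. Define behavior likewise. Use the last pre-dose C-SSRS under SAP 6.2.2, and state the recall period of the pre-dose and post-baseline forms.
2. Add to the SAP table list one C-SSRS shift table by arm, from pre-dose maximum to post-baseline maximum. Tables 14.3.7.3 and 14.3.7.4 can stay.
3. Separately, reconcile the reference in exclusion 17 to a C-SSRS at baseline with Table 1, Protocol 6.1.2 and SAP 6.12.6, which schedule none between screening (Days −28 to −2) and Week 2. How to resolve this is for the sponsor; items 1 and 2 do not depend on it.

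Cost: a few lines of SAP text, one table to program, and a wording clarification in the protocol. Items 1 and 2 use data already collected.
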